make 80% of all health care decisions for the family, shared the SSE brochure with relatives.^{4,6,29,30}

The *long-term goal* of this research is to reduce melanoma mortality by improving self-management of early detection of melanoma. Reduced mortality cannot be proven without effective structured melanoma SSE with partner assistance. One way to achieve partner-assisted SSE is to deliver a uniform self-management program to women who self-identify as at-risk, perform SSE and seek appointments with HCPs for concerning moles. In the absence of ready physician access due to COVID-19, we will test the feasibility of at-home mole self-sampling with a non-invasive adhesive patch used to acquire surface cells of the mole. Our *primary objective*, assessing effectiveness of a SSE education with partner assistance among at-risk women, extends the evidence-based SSE intervention developed among melanoma survivors and their skin check partners (R01CA154908)⁶ and delivers the program to women who had a screening mammogram, which demonstrated the individuals' commitment to health promotion and cancer screening.

STUDY ENDPOINTS:

Aim 1

Primary outcome:

Effectiveness of TMD with SSE will be defined as SSE performance. Further measures of fidelity will be assessed by:

- a) extent of body checked,
- b) recruitment of a skin check partner,
- c) time between noticing a concerning mole, requesting a mole self-sampling kit, and seeking HCP care for a concerning mole, and
- d) SSE sustained by monthly performance over 4 months.

Secondary Outcome:

The effect of TMD with SSE on seeking health care comparing intervention vs control groups for:

- a) inappropriate HCP appointments and skin biopsies for benign conditions, and
- b) appropriate HCP appointments for the clinical diagnosis of atypical (dysplastic nevus) or rule out melanoma and biopsy performed.

Exploratory Aim

Proof-of-concept Outcome:

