Subjects in the intervention arm will monitor new and concerning moles for 4 months by doing monthly skin checks and partner-assisted skin checks (if applicable), record the scores on a scorecard provided in their SSE brochure, and complete the monthly online survey, which asks about changes in mole scores and potential anxiety associated with evolving moles. Subjects will also receive a monthly text message to their personal phone with SSE reminders.

If the subject indicates on their monthly survey or by communicating with the study team, in the form of an email and/or call, that the score of their mole has increased, three options on how to proceed will be offered to the subject. The three choices are as follows: a) continue monthly checking the mole for change, b) receive the mole self-sampling kit to obtain genetic analysis to guide the decision to seek health care, or c) seek an appointment with an HCP.

The mole self-sampling kit contains the materials, directions and a Fed Express or USPS Express mail envelop to overnight the kit to the DermTech laboratory.

Participants may request a kit by email or telephone call to the research team, who will send the kit by Fed Express or USPS Express mail. Within 3-5 business days, the DermTech laboratory will provide the results of the gene analysis online to the PI, [name], who will inform the participant with a written report stating:

- a) the mole is benign, and nothing further is needed or
- b) the mole needs to be biopsied.

If the initial sample has too few cells for analysis, then the participant will be invited to obtain another sample, instructions will be reviewed by telephone or by Facetime with the participant and an additional sample will be obtained.

Participants requiring a skin biopsy will be referred to a local HCP. The research team will develop a participant navigation system for triage to a local HCP, including surgical oncologists, dermatologists, and family practitioners. This triage system will be used to refer participants to schedule an appointment for the skin biopsy within 2-3 weeks. The genetic analysis of the mole will be provided in a letter to the HCP selected by the participant.

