If the option to see the HCP is selected, the research team will assist with locating one and will remind the subject that the HCP may not be available for some time. The study team will not cover the cost of seeing the HCP or cost of treatment recommended by the HCP. The non-payments details are explicitly stated in the consent document.

If the mole(s) requires a biopsy and/or treatment, the EHR will be reviewed to identify diagnosis codes of the mole and review HCP notes.

If throughout the 4 months of active engagement in skin self-examinations, a participant in the intervention arm indicates that they found a concerning mole on their skin check partner while performing a partner skin exam, an opportunity for the concerning mole of the partner to be self-sampled will be offered. For the self-sampling to occur, the subject (the skin check partner) would first be asked eligibility questions to ensure they are over the age of 18 and meet basic eligibility criteria. Once eligibility is established, the partner will be sent an electronic consent form, via REDCap, and complete and sign the form,

indicating they understand what is expected of them as a research participant and the information that was presented to them in the consent document. The same process will be followed for the skin check partner as is in place for the research subject.

Controls (Group 1) will receive a healthy lifestyle brochure and a healthy lifestyle postcard after consenting online and completing baseline assessments. After enrolling in the study, a baseline survey will populate in REDCap, and the subject will be able to download a healthy lifestyle brochure and the postcard reminder. Upon request, the brochure will be mailed. Each month, the subject will receive an email to complete the monthly survey and will receive healthy lifestyle text messages to their mobile phone. The survey they receive will mirror the survey of the SSE intervention arm; therefore, awareness of SSE will be expected to increase, and SSE may be initiated among controls. If a subject indicates that they have found a concerning mole on their monthly survey, the subject will be advised to reach out to their health care provider for further assessment. After completing the final monthly survey, controls will be offered the SSE brochure.

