In order to complete this research before the end of the grant (March 2021), we need to have IRB approval in early May, which will allow EDW to build the lists of eligible subjects. Then we will enroll subjects remotely in June-August 2020 and follow them for 4 months with online surveys (Oct-Dec 2020). Finally, the EHR of HCP visits will be reviewed about 3-4 months after the completion of the last online survey. This additional period of EHR review (Feb 2021- March 2021) gives subjects time to obtain an appointment with their HCP and have a biopsy, if needed.

INCLUSION AND EXCLUSION CRITERIA:

Inclusion Criteria:

- Adult women (aged 18 and older) having a screening mammogram with no upper age limit, who had a screening mammogram from January 1, 2019 to February 28, 2020.
- Able to read English
- Vision enough to read a newspaper
- Self-perception of their potential melanoma risk
- Willing to perform SSE with a skin check partner
- Willing to complete monthly surveys for 4 months and receive monthly text messages to personal mobile phone
- Have home Internet access and smartphone with data plan
- Have access to Federal Express or US Postal Service Express Mail to send mole self-sampling kits
- Willing to allow the research team access to their electronic health record to abstract physician assessment of concerning moles, biopsy results and treatment
- Willing to provide up-to-date email address, mailing address and telephone number

Inclusion criteria of skin check partner to have mole self-sampled

- Male or female over the age of 18 years
- Able to read English
- Vision enough to read a newspaper

Exclusion criteria

- Women under the age of 18 years

- Women overburdened with other co-morbid diseases, medical treatments (e.g., chemotherapy), or cognitive impairment (e.g., by a stroke) as determined by the PI.
- Previous participation in SSE research previously which may be a confounding variable in data analysis

Exclusion criteria of skin check partner to have mole self-sampled

- Male or female under the age of 18
- Unable to read English

VULNERABLE POPULATIONS:

This study will not include the participation of vulnerable populations

PARTICIPANT POPULATIONS:

Accrual Number:	Category/ Group:	Consented: Maximum Number to be Consented or Reviewed/Collected /Screened	Enrolled: Number to Complete the Study or Needed to Address the Research Question
Northwestern Medicine: Prentice Women's Breast Center	Women ≥ 18 years old	500	400

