The research team will be permitted to access study-related, subject-reported information and the EHR of subjects who have a visit with a health care provider for a concerning mole. The EHR of skin check partners will not be accessed. The database that will house this data will only have de-identified data. A unique subject number will replace the use of names in the database. Our systems are guarded against outside entry by Northwestern's own firewall supporting 128-bit encryption. This level of encryption provides the highest level of protection against hackers, computer break-ins, etc. All data is de-identified. Only experienced research team members will work on this study and will have receive training that includes an emphasis upon the importance of confidentiality of information, and all personnel on the project will complete the required NIH training in the protection of human research participants. Physical copies of collected data forms will be retained in separate locked file cabinets and on computers with restricted and password-protected access, without links to the master code list. All data based on the research will be reported in aggregate form. No individual respondents will be identified. Electronic data will be maintained in a study-specific database on the server of the Department of Dermatology at the Feinberg School of Medicine. Paper-based files will be kept in a locked cabinet in a locked room within the Northwestern University Department of Dermatology research offices. Identifiable data will be kept separate from the case report forms and source documents. Data gathered as a result of this study are available to inspection on request by the Food and Drug Administration or other government regulatory agency auditors, and the Northwestern University Institutional Review Board (IRB).

Only approved research personnel will have access to the stored data. The PI is ultimately responsible for the receipt and transmission of the data. As per the Department of Dermatology protocol, data will be retained indefinitely after the completion of the study. All data and other information in this study will be maintained confidentially.

ECONOMIC BURDEN TO PARTICIPANTS:

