- Most recent mammography screening appointment information (date of screening mammogram and location of screening mammogram)

The EHR will be reviewed by the PI for:

- Health care provider notes from visit pertaining to a concerning mole (date of visit, notes from visit, diagnosis code of mole, plan of treatment and/or treatment)

HIPAA Authorization will not be obtained from skin check partners, as the study team will not be viewing their EHR.

QUALIFICATIONS TO CONDUCT RESEARCH AND RESOURCES AVAILABLE:

[name] has been a board-certified physician for over three decades and has conducted an NCI funded R01 and R21 of a similar nature. We will notify the Northwestern University IRB, our project officers, and NCI within 24-48 hours of any serious adverse event. All research assistants have CITI documents on file. Other resources. Lynn Sage Breast Center completes approximately 90,000 screening mammograms each year and Kishwaukee Hospital completes approximately 7,000 screening mammograms/year; therefore, there are adequate numbers of potential subjects to be identified by the EDW search. [name] has full-time research staff and voluntary medical students who fully support this research study at 100% effort. [name] also has weekly meetings with research staff to address any questions regarding the protocol, questions from research subjects, or study related procedures.

MULTI-SITE RESEARCH:

NA

REFERENCES

1. Guy GP, Jr., Thomas CC, Thompson T, et al. Vital signs: Melanoma incidence and mortality trends and projections - United States, 1982-2030. *MMWR Morb Mortal Wkly Rep.* 2015;64(21):591–596.
2. Global burden of disease cancer collaboration, Fitzmaurice C, et al. Global, Regional, and National Cancer Incidence, Mortality, Years of Life Lost, Years Lived With Disability, and Disability-Adjusted Life-Years for 29 Cancer Groups, 1990 to 2016: A Systematic Analysis for the Global Burden of Disease Study. *JAMA Oncol.* 2018;4(11):1553-1568.

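### The rule for opening health records in Procedures Involved is narrower than the secondary outcome and the protocol's other sections, and no section says visits are found the same way in both arms

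*Combined protocol and SAP*

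**What the plan says.** The documents describe review of the electronic health record (EHR) in several places.

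- **Procedures Involved**, after the three options offered to intervention women: "If the mole(s) requires a biopsy and/or treatment, the EHR will be reviewed to identify diagnosis codes of the mole and review HCP notes". The later paragraph on controls does not mention EHR review.
- **Study Timelines**: "the EHR of HCP visits will be reviewed about 3-4 months after the completion of the last online survey". The interval "gives subjects time to obtain an appointment with their HCP and have a biopsy, if needed". The same section allows later contact with women about questions arising from the review of visits for concerning moles.
- **Provisions to Protect the Privacy Interests of Participants**: the team may access "the EHR of subjects who have a visit with a health care provider for a concerning mole".
- **Protected Health Information**: "The EHR will be reviewed by the PI for" provider notes from a concerning-mole visit, including its date, the diagnosis code and the plan. No biopsy condition is attached.
- **Objectives, Aim 1**: providers' clinical or pathologic assessments of concerning moles are to be taken from the Northwestern record.

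The outcomes that depend on this review are in **Study Endpoints**, and each is compared between arms. Outcome (a) covers "inappropriate HCP appointments and skin biopsies for benign conditions". The second outcome, labelled (b), is defined as "appropriate HCP appointments for the clinical diagnosis of atypical (dysplastic nevus) or rule out melanoma and biopsy performed". **Design, Analysis, and Power Calculation** analyses the secondary outcome as whether a woman had any provider appointment in the study period.

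**The concern.** A visit that ends in reassurance, with no biopsy and no treatment, belongs in outcome (a) and in the any-appointment analysis. It does not meet the condition in Procedures Involved, which is the section staff work from. Two abstractors following different sections could therefore return different counts for the same women.

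A second gap lies beneath this one. The documents say whose records may be opened and what is taken from them, but not how the team learns that a visit took place. If it learns through its own contact with participants, ascertainment could depend on arm and on survey response as well as on the care received. The between-arm comparison of appropriate and inappropriate visits is at stake.

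**Working it through.** **1. Which visits each text covers**

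| Visit for a concerning mole | Counts toward | Procedures Involved sentence | Timelines, privacy and health-information sections |
|---|---|---|---|
| Benign, no biopsy or treatment | (a); any appointment | Condition not met | Covered |
| Benign, biopsied | (a); any appointment | Covered | Covered |
| Atypical or rule-out melanoma, biopsied | (b); any appointment | Covered | Covered |

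The texts part on the first row. Outcome (b) requires a biopsy, so the narrower rule leaves it intact and trims only (a). Any resulting error would make visits look more appropriate than they were.

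**2. The plan's own figure**

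Inputs from Design, Analysis, and Power Calculation: 14% versus 21% with any appointment, 1000 women allocated 1:1, 80% power. Alpha is not stated; two-sided 5% is assumed.

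n per arm = [1.96·√(2·p̄(1−p̄)) + 0.8416·√(p₁(1−p₁)+p₂(1−p₂))]² / (p₁−p₂)², with p̄ = 0.175

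= [1.96×0.5374 + 0.8416×0.5351]² / 0.07² = 462, or 490 with continuity correction.

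With 500 per arm, power is 83% uncorrected. The stated figure is reproduced.

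**3. Range if the narrower rule were followed**

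The share of visits that lead to biopsy or treatment is not in the documents. Assume a common share s in both arms and multiply both rates by s:

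| s (assumed) | Rates counted | Power, 500 per arm |
|---|---|---|
| 100% | 14% vs 21% | 83% |
| 75% | 10.5% vs 15.75% | 69% |
| 50% | 7% vs 10.5% | 50% |
| 25% | 3.5% vs 5.25% | 27% |

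These figures concern the any-appointment analysis. They do not measure the effect on outcome (a), for which no rate is planned. If the wider sections are followed, the loss is nil.

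**4. How visits come to the team's notice**

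- The monthly surveys mirror each other across arms.
- Beyond the surveys, intervention women can request kits, receive assay reports and referrals, and get help finding a provider. Study Interventions adds: "The research team will develop a participant navigation system for triage to a local HCP". Controls who report a concerning mole are advised to contact their own provider.
- In the intervention arm, the assay report may itself say whether a biopsy is needed. A kit user told that her mole is benign who still sees a provider is a candidate for (a), yet under the Procedures sentence her record could stay closed. Controls have no assay.
- Retention is expected to be at least 60% at 4 months, so up to 40% of 1000, or 400 women, could have stopped answering surveys.
- The review falls 3–4 months after the last survey, and no survey covers that interval.

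None of these routes is the same for every randomised woman. A common record search would be.

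**The case against.** The strongest reply is that this is one loosely worded sentence. It does not say that records are opened in no other case, and several sections describe review of concerning-mole visits with no biopsy condition. The eligibility criteria also list physician assessment separately from biopsy results. That stands. A reader might infer that no-biopsy visits are excluded altogether, so that this part of outcome (a) would be zero by design. The documents do not support this: it would require the Procedures sentence to override all the others.

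A reader might also take one row of the power table as the expected loss, or assume that most benign visits end without biopsy. Neither has a source in the documents, and outcome (a) itself includes biopsies of benign lesions, which the narrower rule would capture.

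On capture by arm, it is fair to say that no section makes EHR review depend on contact or survey response, and that every woman must accept EHR access to enrol. Differential capture is therefore a risk left open, not an established bias. The same applies to masking. The principal investigator reviews the records and also issues kit results, so knows the arm of kit users. That concerns kit users only (up to 100 specimens), and no effect on classification is shown.

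The point survives because the sections still disagree on a rule that determines a secondary outcome, and none supplies a method of finding visits that is independent of arm.

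**Conclusion.** The point holds as an inconsistency in outcome ascertainment that should be resolved before record abstraction begins. Following the Procedures sentence would undercount outcome (a) and the any-appointment outcome by the share of visits that end without biopsy or treatment. That share is unknown, so the effect runs from nil upward and no single figure is defensible. The power range above rests on an assumed share equal in both arms and on an assumed two-sided 5% test.

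Separately, the lack of a stated, arm-independent way of finding visits leaves room for unequal capture; its direction and size cannot be judged from the documents. The primary outcome, performance of skin self-examination, is not affected, and neither is outcome (b) by the biopsy condition.

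**What to change.** Replace the sentence in Procedures Involved with:

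> For every randomised woman in both arms, the EHR will be searched for HCP visits for a concerning mole, with diagnosis codes and biopsies, from randomisation to the end of the review window, regardless of arm, survey response, assay result or whether a biopsy was done.

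Align the privacy section and Protected Health Information with this text, and fix the search codes before abstraction starts. Where practical, have existing staff remove arm and kit result from the extract before visits are classed as (a) or (b).

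The cost is more records to search and abstract, for about 1000 women. Keeping the search to concerning-mole visits is meant to hold it within the EHR access that eligibility already requires; the consent and authorization wording should be checked against it. The search will not find visits outside the Northwestern record, and the report should state that limit.

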Since most melanomas are visible on the surface of the skin at a curable phase in their evolution, people can perform screening at home with the help of a partner. The annual prevalence of self-reported SSE in the general community ranges from 8 to 21%.²⁰ Women perform more SSE than men.⁷ Women self-detect more than half of melanomas and melanomas detected by women had better prognosis than those detected by men because they were identified at an earlier stage.⁸ The American Academy of Dermatology recognized that 6-50% of melanomas were self-detected;^{21,22} therefore, the Academy encourages self-advocacy thorough routine SSE and regular skin cancer screening for at-risk patients.²³ In a 20 year follow-up case control study of people newly diagnosed with melanoma in 1987-89, skin awareness was associated independently with a decreased risk of melanoma death (HR=0.46, 95% CI=0.28-0.75, $p<0.01$).²⁴ Currently, the median delay in diagnosis, is ~27 months.²⁵ Reports suggest melanomas get about 0.12 mm deeper per month with attendant increasing disease stage.²⁶ A 27-month delay in diagnosis may result in a 0.12 mm deep melanoma (Stage 1A) becoming a 3.24 mm melanoma (Stage 2B with greater risk of metastasis). Time to presentation for care is a key determinant of the patient outcome. Compared with other cancers, melanoma has the longest delays measured as the median time to patient presentation. One goal of this research is to reduce the time from a woman first noticing a “new or changing mole” to examination by a doctor.

Leveraging the Mammogram Screening Encounter.

In the US, women age 50 and older develop the habit of having regular screening mammograms.²⁷ From 50-59 years of age is also when melanoma incidence in women increases.²⁸ In Illinois, screening mammograms may be scheduled without a physician's order, thus, women who do not have regular care with HCPs may obtain mammograms. One of the innovations of our proposed study, as described below, is using the screening mammography encounter as an opportunity to educate women of all races and ethnicities at the point in their lives when melanoma is most likely to develop. In our pilot feasibility research, we leveraged mammogram screening encounters to reach women, who were not aware of their melanoma risk.⁴ Women, who are the nexus of familial communication of health information and social support in their own homes and

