Contact information for potential subjects, who will be women who had a screening mammogram from January 2, 2019 until February 28, 2020, will be obtained from the Northwestern Medicine Electronic Data Warehouse (EDW). Based on our experience, women with a history of breast cancer will be excluded because the focus of their health care is on treatment of breast cancer. Subjects will be emailed a recruitment email explaining the research study regarding skin cancer prevention and skin self-examinations. Subjects will receive a link to the online REDCap program that offers electronic consent, randomization, and self-reported surveys. After remotely enrolling in the study, and completing the baseline questionnaire, the subjects will be randomized 1:1 between intervention and control arms. Intervention arm participants will receive the SSE brochure. The SSE brochure discusses basic information about melanoma, how to identify a melanoma, the importance of a skin check partner, and gives a diary for tracking monthly changes in moles via a provided scorecard. The provided postcard maybe printed by the woman and affixed to a location in their homes to capture their attention and remind participants to perform SSE. Subjects will invite a skin check partner to help score the border, color, and diameter of a new and/or concerning mole(s) using a provided scoring system for their 4 months of study participation. While a skin check partner will be beneficial to perform SSE, a skin check partner is not an absolute requirement to participate in this research. The scoring system uses a scale of 1-3 (1= normal, 2= unsure, 3= not normal). In the brochure, color examples of normal and abnormal features illustrate the scoring rules. The decision rules about seeking health care are based on the cumulative score of three features of the mole: 3 = benign, stop checking the mole; 4-7 = check the mole in one month; 8-9 = make an appointment with a doctor to have the mole checked in about 2-3 weeks, which is the standard of care for evolving moles. In the absence of physician access (COVID-19), the decision rules used in our prior research will be modified to:
8-9= perform mole self-sampling to determine if the mole needs to be biopsied.

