a printed brochure will be mailed. Participants will receive monthly reminders via email and text messaged to their personal phone to perform SSE, to encourage engagement and retention. In addition, a monthly REDCap survey will be sent to the subject's email. This monthly survey will include goal setting and reminders to engage a skin check partner to help check skin in hard to see areas and to assist with the monitoring of any concerning moles and new moles. Tracking of specific details and changes of concerning and new moles will be documented on the provided scorecard in the brochure. If the score of the mole increases, which is indicated on the monthly survey or via email and/or phone, three options on how to proceed with the concerning mole will be provided to the subject.

-Option 1 is to continue monitoring the mole monthly for change.

-Option 2 will be to perform mole self-sampling with the kit to collect a sample of surface cells of the concerning mole with four adhesive patches for gene analysis to help decide about seeking further health care for biopsy of the mole. Of note, physician collected samples tested for *LINC* and *PRAME* gene mutations differentiated melanoma and melanoma in situ from benign moles and were confirmed histologically with 91% accuracy.

-Option 3 will be to seek an appointment with a health care provider.

If mole self-sampling is selected, the kit with the subject number as ID (blinded for personal identifying information), directions, and postage for the kit to be sent to the company that created this self-sampling kit, DermTech, will be provided. Upon completing the mole self-sampling and mailing the specimen to the DermTech laboratory, it will take 3-5 days for the results to be provided to the PI, [name], in the form of a secure online portal. The subject will not obtain their gene test results from the DermTech laboratory. [name] will provide written test results to the participant with the option of discussing the results with a telephone call. A referral will be made to the HCP to perform a skin biopsy if needed. The DermTech self-sampling kit is approved for use but requires ordering by a licensed HCP, who will be [name], the PI.

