Design, Analysis, and Power Calculation with Target Enrollment Justification

For the RCT, participants will be randomly assigned to receive the SSE intervention or control (healthy lifestyle) in a 1:1 ratio. This will result in approximately 500 participants in each group. The primary analysis will be intent to treat, with data imputed one of two ways. First, we will run a “worse-case scenario” where all drop-outs will be assumed to not be performing SSE. Second, we will create 5 imputed data sets for missing data based on all available data and analyze with PROC MIANALYZE to obtain valid statistical inferences. From previous work, we expect at least 60% retention at 4 months.

We will use GLMM with a logit link to test if the intervention affects the rate of SSE, while adjusting for the repeated measures within individuals over the first 4 months. Using these repeated measures, and assuming an autocorrelation of 0.9, a total sample of 1000 would enable us to detect an increase from 80% of SSE in the control group to 86.3% in the intervention group. Assuming only 10% discordance, a sample of 500 control women provides 80% power to detect an increase of 7%, while the remaining 3% cease SSE. Additional fidelity measures in Aim 2 will be combined to score an overall standardized fidelity score at each time. If the mean fidelity score is 80%, a sample of 500 women provide enough information to produce a 95% Confidence interval with a width of 0.09. The sample for 500 intervention women provides 80% power to detect declining fidelity or sustainability of monthly SSEs as a standardized slope of 0.13. The secondary outcome of seeking HCP appointments for a necessary mole will be analyzed with generalized linear models, as described above, but considering the outcome as “any HCP appointment” during the study time frame. Previous data suggests that approximately 14% of women should contact HCP for an appointment, and our sample of 1000 women provides 80% power to detect a baseline rate in the control group as small as 21%.

Plans for securing the data is in the “provisions to protect the privacy interests of participants” section of the protocol.

PROVISIONS TO MONITOR THE DATA TO ENSURE THE SAFETY OF PARTICIPANTS:

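### The control survey is to mirror an intervention survey that contains goal setting and partner reminders, with no limit to outcome items; taken literally, this pulls the SSE contrast toward no effect

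*Combined protocol and SAP*

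**What the plan says.** All places are in the combined protocol and SAP.

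- **Intervention survey, prompts** (PROCEDURES INVOLVED, Group 2): "This monthly survey will include goal setting and reminders to engage a skin check partner to help check skin in hard to see areas". The same sentence extends the reminders to help with monitoring concerning and new moles. SSE reminders by email and text are listed separately, so these prompts belong to the survey itself.
- **Intervention survey, measurement** (STUDY INTERVENTIONS): participants "complete the monthly online survey, which asks about changes in mole scores and potential anxiety associated with evolving moles".
- **Control survey** (PROCEDURES INVOLVED, Group 1): "The survey they receive will mirror the survey of the SSE intervention arm; therefore, awareness of SSE will be expected to increase". The sentence goes on to accept that some controls may start SSE.
- **Stated differences for controls** (same paragraph): a healthy lifestyle brochure, postcard and texts, and advice to contact their own provider about a concerning mole. Also, "After completing the final monthly survey, controls will be offered the SSE brochure".
- **Outcomes** (STUDY ENDPOINTS): SSE performance is the primary outcome, and recruiting a skin check partner is a listed fidelity measure. Aim 1 compares SSE sustainability with controls.
- **Power** (Design, Analysis, and Power Calculation): 1000 women in total, to "detect an increase from 80% of SSE in the control group to 86.3% in the intervention group". A further calculation for 500 control women has 10% discordance, split into a 7% increase and 3% who cease SSE.

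**The concern.** Goal setting and partner reminders are meant to change behaviour. Comparing SSE between arms needs the same questions in both arms, asked at the same times. It does not need the prompts. If controls receive the prompts every month, part of the intervention reaches the comparison group and acts on the primary outcome. The expected difference shrinks, and a null result becomes hard to read: it could mean that the education does not work, or that both arms received an active part of it. Partner recruitment is exposed in the same way if it is compared between arms, because the reminders are about engaging a partner.

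Reactivity from being asked about SSE each month is a different matter. It cannot be avoided in a survey-based trial and is not the complaint.

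**Working it through.** **1. Does anything remove the prompts from the control survey?**

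| Element | Intervention arm | Control arm | Takes prompts out of the control survey? |
|---|---|---|---|
| Brochure and postcard | SSE | Healthy lifestyle; SSE brochure offered after the last survey | No, separate material |
| Text messages | SSE reminders | Healthy lifestyle | No, separate channel |
| Concerning mole reported | Three options | Advised to contact own provider | No, this governs the response to an answer |
| Monthly survey | Mole scores, anxiety, goal setting, partner and mole-monitoring reminders | Mirrors the intervention survey | No exclusion stated |

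The only sentence on the content of the control survey is the mirroring sentence, and it makes no exception.

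**2. Direction.** If controls receive the prompts and respond to them, control SSE rises, the intervention rate is unaffected, and the difference narrows. The effect is toward no difference.

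**3. The plan's primary figure.** Inputs from the power section: 80% against 86.3%, 500 per arm, four measures, autocorrelation 0.9. Assumed because not stated for this contrast: two-sided alpha 0.05, target power 80%. I also assume no loss.

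- Variance factor for the mean of four measures: exchangeable (1 + 3 × 0.9)/4 = 0.925; AR(1) [4 + 2(3 × 0.9 + 2 × 0.81 + 0.729)]/16 = 0.881.
- Sum of variances: 0.80 × 0.20 + 0.863 × 0.137 = 0.2782.
- Standard error: √(0.2782 × 0.925/500) = 0.02269, or √(0.2782 × 0.881/500) = 0.02214.
- Power: Φ(0.063/0.02269 − 1.96) = 79.3%, or Φ(0.063/0.02214 − 1.96) = 81.2%.

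The stated figure reproduces. It sits close to 80% power, so there is little room for a narrower difference. How much narrower it might be cannot be calculated, because no document gives a size for carry-over.

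**4. The control-arm calculation.** I read this as a paired (McNemar-type) test of change within controls: n = 500, 7% start, 3% cease, two-sided alpha 0.05 assumed.

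- Difference 0.07 − 0.03 = 0.04; discordance 0.07 + 0.03 = 0.10.
- Power = Φ[(0.04 × √500 − 1.96 × √0.10)/√(0.10 − 0.04²)] = Φ[(0.8944 − 0.6198)/0.3137] = Φ(0.875) = 80.9%.

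This agrees with the plan's 80%. The plan therefore appears to expect some uptake among controls and to be able to detect it. The test would give net change in the control arm. It would not keep the prompts away from controls, and it could not separate their effect from that of the questions.

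**The case against.** The best defence is that mirroring means parallel questions, not a copy. A literal copy would not work: the intervention survey asks about mole scores kept on a scorecard in the SSE brochure, which controls are offered only at the end. Where the control paragraph does specify content, it keeps it apart from SSE material. The goal setting is described only under Group 2. The expected rise in SSE awareness is explained well enough by asking controls about SSE each month. This is a reasonable reading and may be the intended one, but the text does not say so, and a REDCap build would be made from the text.

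Second, the plan openly accepts SSE uptake among controls and seems to have powered a test of it. That stands as disclosure, and it shows that uptake was considered. It does not explain why controls would need goal setting or reminders.

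Third, every participant meets the idea of SSE before randomisation: "Subjects will be emailed a recruitment email explaining the research study regarding skin cancer prevention and skin self-examinations", and eligibility requires being "Willing to perform SSE with a skin check partner". The added effect of survey prompts may therefore be small. This stands, although one exposure at entry is not the same as monthly prompting.

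Fourth, any bias is toward no effect, so it would not produce a false claim of benefit. That is true, but a diluted contrast is still a cost to a trial whose aim is to show effectiveness.

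**Conclusion.** The point holds as a minor one, with low to medium confidence. The wording permits behaviour-change prompts for the primary outcome to reach controls every month, and measurement does not require this. The direction is toward no effect. The size cannot be derived.

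The conclusion rests on mirroring being taken literally and on controls responding to the prompts. Neither can be confirmed without the survey forms.

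A reader might go further in three ways that the documents do not support:

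- **That controls do receive the intervention content.** The text allows this but does not show it.
- **That power falls by a stated amount.** Any leakage fraction would be invented. If the 80% control rate already allows for SSE prompted by the survey, planned power is unchanged, and only the meaning of the contrast changes.
- **That the 7% and 3% in the control-arm calculation forecast contamination.** They describe a change that the sample could detect. They are not a predicted amount, and they are not attributed to survey prompts.

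**What to change.** In the control paragraph of PROCEDURES INVOLVED, replace the mirroring clause with a statement that the control survey *will contain the same outcome items as the survey* of the intervention arm. Add that goal setting and the partner and mole-monitoring reminders are shown to the intervention arm only, and implement this as an arm-based REDCap branch.

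The cost is one branch and a sentence or two. The forms seem to have to differ already because of the mole-score items. The downside is slightly different forms by arm, and reactivity from asking about SSE remains. If the prompts were never meant for controls, the change of wording is enough.

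As an optional clarification, the power section could say whether the 80% control rate allows for SSE prompted by the survey questions.
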